The overall Specific Aim of this proposal is to determine the effect of opioid taper on pain sensitivity in patients with chronic pain. Specifically, in a well-characterized sample of men and women with chronic neuropathic pain and receiving high-dose opioid therapy (200mg morphine equivalents/day [MED]), experimental pain responses will be serially described over the course of an individualized opioid taper to a safer dose of 90mg MED for up to 12 months. Changes will be inspected within-subject over time, and pain perception will be measured with two valid and reliable experimental pain induction techniques commonly used to measure OIH (cold-pressor, quantitative sensory testing); in addition, related functional improvements and subject-level predictors of response will be described. Hypothesis 1. Subjects undergoing opioid taper will have improved pain responses over time compared to within-subject baseline as measured by cold-pressor and quantitative sensory pain testing. Hypothesis 2. Improvements in experimental pain responses will be positively related to improved functional outcomes compared to within-subject baseline as measured by the PROMIS physical, mental and social health measures. Hypothesis 3. Degree of improvement in experimental pain responses related to opioid taper will be predicted by demographic, pain, and opioid use history characteristics of the subject. Data showing that pain perception improves as opioids are withdrawn would provide an evidence-based, mechanistic rationale for opioid taper in patients with chronic pain and have the potential to support a sea-change in opioid prescription practices. In that ongoing opioid therapy brings with it significant health risks for the patient and the community, it is critical that empirical evidence of its efficacy be demonstrated to balance the benefits with the risks of adverse events, potential misuse and abuse, and patient safety.

Primary outcome variable(s)

The primary dependent variable, pain perception, will be measured using two highly reliable and valid pain induction techniques, the cold-pressor test (CPT) and quantitative sensory testing (QST), employing procedures consistent with those described in the literature. Order of pain testing will vary, and three aspects of the pain response will be captured at each study session: evoked pain; temporal summation; and conditioned pain modulation, which map on to the hypothesized peripheral, spinal and supra-spinal mechanisms of OIH.

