
Study Design

Phase*

Not applicable

Design

A prospective time-series survey design will be utilized to measure the experimental (CPT and QST) pain responses of chronic pain patients on high-dose opioid therapy (200mg MED) prior to and then regularly during and following a voluntary opioid taper. Data will be collected weekly during the active taper period; once the subject has reached a stable maintenance dose (90 MED), assessments will occur monthly until month 12. Because our previous work has shown stability in pain responses in patients on

high-dose opioid therapy over time (6 months), and the clinical imperative of tapering patients to safer doses, a control group of patients maintained on high-dose therapy is not included. Consistent with expert opinion in the field, a longitudinal within-subject design is planned.

Study duration

The overall duration of the study is two years, during which time all subjects will be enrolled and complete the study. Data will be collected weekly during the active taper period; once the subject has reached a stable maintenance dose (less than or equal to 90 MED), assessments will occur monthly until month 12. If funded, the study would begin Oct 1, 2018.

Resources necessary for human research protection

Describe research staff and justify that the staff are adequate in number and qualifications to conduct the research. Describe how you will ensure that all staff assisting with the research are adequately informed about the protocol and their research related duties. Please allow adequate time for the researchers to conduct and complete the research. Please confirm that there are adequate facilities for the research.

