Participants will be recruited from those treated at the large and nationally-renowned Penn Pain Medicine Center at the University of Pennsylvania Penn Medicine Neuroscience Center. The Penn Pain Medicine Center provides interdisciplinary, multimodal pain care to over 12,000 outpatients annually, an estimated 20% of whom are taking opioids on a regular basis. At any one point in time an estimated 50 patients are undergoing opioid taper, up to half of whom are tapered from opioid doses greater or equal to 200mg MED. Due to anticipated rates of dropout, 25% oversampling for these individuals is planned. Results from previous studies have demonstrated moderate to large effect size estimates of opioids on cold-pressor and QST experimental pain responses. Based on these estimates, a sample size

of 25 will have over 99% power to detect differences in outcome. Using an alpha of 0.05/4 (Bonferroni correction) to account for multiple outcomes, we will have over 90% power to detect significant changes at the 0.01 level for all of the outcomes. Cross-sectional and prospective studies demonstrate statistically significant differences in experimental pain responses with changes between 80-90mg MED (10,11,70); since MED decreases in the proposed work will be 110 MED (tapers from 200MED to 90MED), we anticipate having no difficulty discerning taper effects on pain responses.

Key inclusion criteria

(1) between ages of 21-60; (2) documented chronic neuropathic non-malignant pain condition of at least one year duration; (3) on 200mg MED for at least 6 months; (4) have fully engaged in all prescribed non-opioid pain management treatments; (5) willing to undergo prescribed opioid taper; (6) otherwise in good physical and mental health, or in the care of a physician who is willing to take responsibility for such treatment; and (7) able to understand the purpose and instructions of the study, and provide informed consent as approved by the University of Pennsylvania IRB.

Key exclusion criteria

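### Holm's step-down procedure, written into the Analysis Plan with a named family, would keep the same 5% familywise error as the Bonferroni split used for sizing and never reject less

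*Combined protocol and SAP*

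**What the plan says.** The protocol's Accrual section describes the expected effects only in words: "Results from previous studies have demonstrated moderate to large effect size estimates of opioids on cold-pressor and QST experimental pain responses". It then states that a sample "of 25 will have over 99% power to detect differences in outcome". Multiplicity enters in the next sentence, "Using an alpha of 0.05/4 (Bonferroni correction) to account for multiple outcomes", which goes on to claim that "we will have over 90% power to detect significant changes at the 0.01 level for all of the outcomes". The same section says "Due to anticipated rates of dropout, 25% oversampling for these individuals is planned", without saying whether the 25 already includes that allowance.

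The Analysis Plan specifies a separate mixed model for each pain and functional outcome. It gives no adjusted significance level, no family of hypotheses, no testing order and no multiplicity procedure.

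The four outcomes behind the divisor are not identified. The primary outcome section says that "three aspects of the pain response will be captured at each study session: evoked pain; temporal summation; and conditioned pain modulation", which makes three. The Procedures section divides evoked pain further, into threshold, tolerance and maximal intensity.

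**The concern.** A Bonferroni split tests each outcome at 0.05/4 = 0.0125 regardless of what the other outcomes show. Holm's procedure starts at the same threshold and relaxes it after each rejection, with the same protection against any false positive. If 0.05/4 were carried into the analysis unchanged, a study of 25 people would have less power on its second, third and fourth findings than it could have.

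Those later findings matter here. The protocol ties the three aspects of pain response to peripheral, spinal and supra-spinal mechanisms, and Hypothesis 1 covers both cold-pressor and quantitative sensory testing. The study wants to learn which aspects change, not only whether one does. Because the Analysis Plan has no rule yet, this is also the time to choose one.

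**Working it through.** **Inputs from the documents.** n = 25; per-outcome level 0.05/4 = 0.0125; stated powers above 99% unadjusted and above 90% adjusted (the adjusted figure is quoted at 0.01, not 0.0125); a single group in which "a longitudinal within-subject design is planned".

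**Assumptions, because the documents give no figure.** Standardised within-subject change d from 0.5 to 0.9; equal correlation of 0.2 to 0.5 between outcomes; two-sided tests; paired t-tests in place of the planned mixed models; 0.05 as the unadjusted level. If the 25 includes the oversampling, about 25/1.25 = 20 subjects complete.

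**Step 1. The plan's own powers.** They cannot be reproduced directly, since no effect size, SD or sidedness is given, so d has to be back-solved. Power is the probability that a noncentral t variable with n − 1 degrees of freedom and noncentrality d√n exceeds the two-sided critical value (the opposite tail is negligible). For n = 25 the critical values on 24 degrees of freedom are 2.064 (level 0.05), 2.700 (0.0125) and 2.797 (0.01).

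| d | d√25 | power at 0.05 | at 0.0125 | at 0.01 |
|---|---|---|---|---|
| 0.5 | 2.5 | 67% | 44% | 40% |
| 0.8 | 4.0 | 97% | 89% | 87% |
| 0.9 | 4.5 | 99.1% | 95.6% | 94.6% |

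Both stated powers hold together at d of about 0.9. At a moderate d = 0.5 neither does.

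**Step 2. The two rules.** Order the p-values from smallest to largest. Holm compares them in turn with 0.05/4 = 0.0125, 0.05/3 = 0.0167, 0.05/2 = 0.025 and 0.05, and stops at the first failure. Bonferroni compares all four with 0.0125. Every Holm threshold is at least 0.0125, so any outcome Bonferroni rejects is also rejected by Holm. The first thresholds coincide, so the chance of at least one rejection is identical.

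**Step 3. Familywise error.** In simulation with no real effects (n = 25, four outcomes), both rules gave 5.0% at correlation 0 and 4.5% at correlation 0.5. With one real effect of 0.8, the chance of a false rejection among the other three was 3.7% (Bonferroni) and 4.8% (Holm) at correlation 0, and 3.4% and 4.3% at correlation 0.5. Holm uses error that Bonferroni leaves unspent and stays within 5%.

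**Step 4. Power with all four effects real and equal, n = 25.** Ranges are over correlation 0.2 to 0.5.

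| d | average per outcome, Bonferroni | Holm |
|---|---|---|
| 0.5 | 44% | 53% |
| 0.6 | 62% | 73–74% |
| 0.8 | 89% | 95–96% |
| 0.9 | 96% | 99% |

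The chance of detecting all four rises from 66–72% to 88–90% at d = 0.8, and from 85–87% to 96% at d = 0.9. With 20 subjects, average power per outcome goes from 33% to 39–40% (d = 0.5), 49% to 59% (0.6) and 78–79% to 88–89% (0.8).

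**Step 5. Fewer real effects, d = 0.8, n = 25.** Average power for the real effects:

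| real effects | Bonferroni | Holm | gain |
|---|---|---|---|
| four | 89% | 95–96% | 6–7 points |
| three | 89% | 93% | about 4 |
| two | 89% | 91% | about 2 |
| one | 89% | 89% | about 0 |

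**The case against.** A reader might infer from the Accrual sentence that the analysis will test every outcome at 0.05/4 whatever the others show, and that the plan therefore discards power. The documents do not support that. The phrase is a sizing assumption, and the Analysis Plan commits to no rule. Sizing at 0.05/4 is fully compatible with Holm at analysis. This objection stands, and it moves the point from replacing a rule to writing one.

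A reader might also infer that Bonferroni is a mistake, or that its cost buys nothing. Neither follows. It is a valid procedure, and it comes with simple simultaneous confidence intervals that agree with the tests, which Holm does not. In a self-described observational pilot that is a real consideration.

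The size of the gain can fairly be questioned too. It is largest when all four effects are real. The documents do not say that the three aspects should move together; they link them to different mechanisms, so a change in only one is plausible, and then Holm adds almost nothing. At the d of about 0.9 that fits the plan's own powers, the gain per outcome is only about 3 points. The larger gains at 0.5 and 0.6 lie where the stated power already fails, which is a separate problem.

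What is left is narrower. Holm never does worse on the tests, the documents give no numeric effect size that would secure d = 0.9, and even there the chance of detecting all four outcomes improves by about 9 to 11 points.

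**Conclusion.** The point holds as an inexpensive improvement. The only stated adjustment is Bonferroni at 0.05/4, in the power statement, and the Analysis Plan has no multiplicity rule. Holm would give the same familywise protection with equal or greater power.

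With 25 subjects and all four effects real, the gain per outcome is roughly 6 to 12 points for d between 0.5 and 0.8 and about 3 points at 0.9. It falls towards zero as fewer effects are real, and the probability of at least one significant result is unaffected.

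These figures rest on assumed effect sizes, correlation and two-sided testing, and on paired t-tests in place of mixed models with random slopes and many visits. The ordering of the two rules does not depend on those assumptions; the size of the gain does. Nothing here shows that conclusions drawn under Bonferroni would be invalid.

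**What to change.** In the Analysis Plan, list by name the Hypothesis 1 outcomes that form the family, and reconcile their number with the divisor of four and with the three aspects in the primary outcome section. Then state that they will be tested by Holm's step-down procedure at a familywise level of 0.05. Either procedure needs the named family, and Holm's thresholds follow from its size.

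If the family stays at four, the sizing at 0.05/4 can stand, because it is Holm's first step. The power sentence should then quote 0.0125 consistently instead of 0.01. If the family has another size, the divisor in the power statement should be updated to match.

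The cost is a short list and one sentence on the rule, with no change to subjects, visits, data or software. The downside is that Holm has no simple matching simultaneous intervals; Bonferroni intervals can be reported alongside, with a note that they may include no change for an outcome that Holm rejects.

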Prescription Opioid Abuse Epidemic The United States is in the midst of a growing and dangerous epidemic of prescription drug abuse. Of the 1 in 3 Americans who used a prescription opioid in 2015, 11.3 million reported misusing the medication(37) with 1.9 million meeting diagnostic criteria for opioid use disorder (OUD).(38) The Centers for Disease Control and Prevention (CDC)(39) reported that 44 people in the U.S. die from overdose of prescription opioids daily, a number which has nearly quadrupled since 1999.(40) Further, the rapid rise of heroin and illicit fentanyl overdose in US has been tied to prescription opioid abuse; 45% of people who use heroin were also addicted to prescription opioid analgesics.(40,41) This public health crisis has been fueled in part by the large supply of opioids being prescribed in our communities. The quantity of prescription opioid analgesics sold to pharmacies, hospitals, and doctors offices was 4 times greater in 2010 than in 1999(39), and in 2016, clinicians wrote an estimated 215 million prescriptions for opioid analgesics.(42) Critical to addressing problematic prescribing practices is the development of safe and evidence-based practice guidelines for the use of opioids in the treatment of chronic pain. **Need for Evidence-based Opioid Prescribing** In 2016, the CDC released the Guideline for Prescribing Opioids for Chronic Pain(32), which targeted opioid analgesic prescribing practices as an important means to reduce prescription opioid abuse, OUD, and overdose deaths. Although the guideline included strategies to decrease risk, evidence to support the efficacy of the CDC recommendations is lacking.(20) It reflects concern at the federal level that healthcare providers are overprescribing these medications, particularly for chronic pain. In fact, it is currently estimated that between 5-8 million Americans use opioids on a daily basis for chronic pain relief(20), with a recent analysis showing that over half of all opioid prescriptions written in the VA system are for veterans with chronic pain.(43) Yet, opioid therapy for chronic pain is not an evidence-based intervention. In a recent review, Von Korff(44) argues that outcomes are actually poorer for chronic pain patients on opioid therapy in comparison to those not taking opioids on multiple indicators including functional status, quality of life, return to work, and self-reported disability.(45-47) Recent NIH reviews conclude that evidence for long-term benefits with daily opioid use is limited.(33,48,49) These analyses have prompted renewed calls for tapering patients off opioid therapy(36,50,51), citing reports of decreased pain, improved function and better quality of life.(21,22,51-58) **Potential Benefit of Opioid Taper Reduction of Opioid-induced Hyperalgesia (OIH)?** There are multiple mechanisms by which opioid taper might improve chronic pain outcomes. A theorized contributor to poor pain relief in this population is the presence of opioid-induced hyperalgesia (OIH)(25,26), defined as a counterintuitive increased sensitivity to pain related to ongoing opioid use.(59,60) Best described in samples of opioid abusers, cross-sectional data suggest a large effect size, indicating that opioid-dependent subjects are 42%76% less tolerant of experimental pain than are matched controls. (29-31,61-63) Cross-sectional data suggest the presence of OIH in chronic pain patients, showing those on opioids to have poor tolerance for experimental heat, cold and pressure pain.(2-11) Assuming a causal relationship between opioids and hyperalgesia, it is hypothesized that tapering opioids would diminish OIH and thereby improve pain responses in patients with chronic pain. Group comparisons reveal that detoxified opioid addicts are more tolerant of experimental pain than those on opioid maintenance therapy(61-65), and with respect to patients with pain, case studies of those with chronic (66,67) or cancer(68-73) pain show significant pain improvement within hours of opioid dose reduction. Conversely, decreased tolerance to experimental thermal pain has been demonstrated in prospective studies of patients with chronic pain following 1-6 months of opioid therapy.(74-76) **Characterization of Effect of Opioid-taper on Pain and Function** Thus, although there is evidence that patients do better following opioid taper, the degree to which improvements are due to resolution of OIH is unclear. The findings described above suggest that a clearer description of the effect of opioid taper on pain perception is needed, including description of relationship to functional outcomes and identification of subject-level predictors. **Relationship to functional outcomes.** As noted, accumulating evidence suggests that chronic pain, function and quality of life improve as patients successfully taper their

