Standard of Care: In light of the demonstrated health risks associated with daily opioid doses greater than 90mg MED, current practice at the Penn Pain Medicine Center is to taper all chronic pain patients down to or below this MED and to stabilize on the lowest effective dose as agreed upon by the patient and prescriber. The actual rate of taper varies with tolerability and availability of dosages of opioid, but averages 10-15% decrease/month. Final stabilization dose also varies between patients but the goal to achieve a daily dose of 90mg MED. Prior to attempting taper, an adequate trial of all non-opioid and non-pharmacologic interventions are provided so that the patients chronic pain is under maximal control. Research Purposes: Baseline Study Session: Study data collection will begin immediately following consent, with the collection of urine toxicology, chronic pain and opioid use history, and baseline pain testing (see attached Data Collection Schedule). It is expected that it will take 30min to complete the baseline measures and another 30min to perform the pain testing battery, totaling 60min for the first session; subsequent sessions should last no longer than 30min. Study Sessions. All data collection will take place in a private office located in the Penn Pain Medicine Center, with sessions scheduled within 3hrs of morning opioid dose, and subjects instructed to ingest no caffeine or nicotine for 1hr prior to each session. Concurrent medication use since last visit, and last menstrual period date for female participants will be documented. A withdrawal score and urine sample for toxicology will be collected immediately prior to pain testing to verify compliance with opioid treatment. Sessions will be scheduled to coincide with regular clinic visits as possible. All study data will be collected using REDCap (Research Electronic Data Capture), utilizing PhenX data collection tools as available. Pain Responses: The primary dependent variable, pain, will be measured using two highly reliable and valid pain induction techniques, the CPT and QST, employing procedures consistent with those described in the literature. Order of pain testing will vary, and three aspects of the pain response will be captured at each study session: evoked pain; temporal summation; and conditioned pain modulation, which map on to the hypothesized peripheral, spinal and supra-spinal mechanisms of OIH. Protocols for each assay have been uploaded. Evoked pain perception: The CPT apparatus consists of a circulating water bath maintained at $1^{\circ}\text{C} \pm 0.5^{\circ}\text{C}$, into which subjects immerse their dominant hand and forearm to elicit a nociceptive response. Elapsed time until pain threshold and tolerance are reached measures evoked pain. A stopwatch is simultaneously activated with arm immersion, and subjects instructed to indicate when the cold sensation becomes a painful sensation (pain threshold), and when the pain becomes subjectively intolerable or spontaneous hand removal (pain tolerance). Immediately after hand withdrawal, subjects are asked to mark maximal pain intensity on a computerized visual analogue scale (Co-VAS, 0-100). Temporal Summation (TS): As a component of QST, a thermal testing analyzer (TSA; Medoc TSA-2001 device) with a sized 30 x 30 mm Peltier thermode, is used for the assessment

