
The following documents are currently attached to this item:

Procedures (datacollectionschedule.docx)

Procedures (appacoldpressortestinginstructionsandscrip.docx)

Procedures (appbquantitativesensorytestinginstructionsandscrip.docx)

Deception

Does your project use deception?

No

International Research

Are you conducting research outside of the United States?

No

Analysis Plan

Preliminary Analyses. Preliminary analyses will include generating descriptive statistics for all baseline measures to characterize the sample, including measures of central tendency and variation for continuous variables; for dichotomous/categorical variables, measures will include frequencies and percentages. Distributional properties will be examined to determine if variance stabilizing or normalizing transformations are required. Non-inferential interim analyses will be performed to ensure data collection and archiving procedures are operating correctly. Outliers will be assessed by visual inspection and checked for accuracy. Normality will be assessed using Shapiro-Wilk tests; should violations emerge (i.e., cold-pressor data are anticipated to be bimodal), transformations or non-parametric tests will be used. Due to known differences in pain responses between men and women, sex

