as a biological variable will be considered in all analyses. Statistical Analyses. The effect of opioid taper on changes in pain responses (CPT, QST), and functional outcomes (PROMIS domains) over time will be examined using longitudinal mixed-effects regression modeling, using general linear regression modeling with regularization as a function of baseline dose, end dose, and taper rate. These longitudinal profiles will be examined using a linear mixed effects framework with SAS Proc Mixed in which all available data collected during follow-up are used. Mixed models can account for the correlation between repeated measures and handle non-excessive missing data better than traditional models and allow for use of time-independent and time-dependent covariates. To assess patterns of attrition over time, a comparison of withdrawal rates and time to withdrawal will be included. Separate mixed effects regression models will be generated for each of the continuous outcome measures of interest (pain responses, functional outcomes). Random slopes and intercepts will be modeled to represent the participant-level deviation from the fixed-effect slope over time and intercept, respectively. Restricted maximum likelihood estimation will be used and the most appropriate covariance structure examined. Scores will be analyzed as repeated observations of the dependent variable, with mean-centered baseline outcome scores serving as a covariate. Other predictor variables will include baseline demographic characteristics of the patient, severity and chronicity of pain suffered, and opioid use history. Baseline measures will be analyzed as time-independent covariates. The Akaike information criterion will be used to evaluate overall model fit and to select the best-fitting longitudinal change pattern. .

The following documents are currently attached to this item:

There are no documents attached for this item.

Data confidentiality

- x Paper-based records will be kept in a secure location and only be accessible to personnel involved in the study.**
- x Computer-based files will only be made available to personnel involved in the study through the use of access privileges and passwords.**
- x Prior to access to any study-related information, personnel will be required to sign statements agreeing to protect the security and confidentiality of identifiable information.**
- x Wherever feasible, identifiers will be removed from study-related information.**

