Cold-Pressor Pain Induction (CP): As it will induce acute pain, the cold-pressor (CP) procedure will cause the subject discomfort. Subjects will be assured via the consent process that they may discontinue their study participation at any time if they decide not to undergo the painful experience. The PI has performed these pain induction techniques on close to 200 subjects in past research endeavors without a single adverse event. Throughout the pain procedures, vital signs will be continuously monitored and staff available to communicate any discomforts they may experience. Potential CP risks to the subjects are minimal; injury including tissue damage is unlikely as exposure time is to be short (5min); the subject can remove the hand from the ice water should it become subjectively intolerable and all trials will be truncated at 300 seconds. No adverse effects have been reported with the CP pain induction technique in over 75 years of published research. Quantitative sensory testing Pain Induction (QST): Like the cold-pressor procedure, the QST is designed to induce acute pain, thus will cause the subject discomfort. Subjects will be assured via the consent process that they may discontinue their study participation at any time if they decide not to undergo the painful experience. Vital signs will be measured before and after the test, and study staff available to communicate any discomforts they may experience. The heat devices are designed not to exceed safe temperatures and have automatic shut-off. Potential risks to the subjects are minimal, which include a burn such as a bad sunburn. These happen very infrequently (1%). Breach of Confidentiality: Participation in this study may constitute a social risk to the participant in that others may learn that he or she takes opioids regularly for chronic pain. Due to the sensitive nature of this information, privacy and confidentiality will be strictly maintained in all aspects of participation. Testing sessions will take place in private rooms where strict privacy is enforced and all research and clinical staff are HIPAA certified.

Potential Study Benefits

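### Cold-pressor tolerance is cut off at 300 seconds but modelled as an ordinary continuous outcome, so a shift in a common direction is understated to the extent that trials reach the limit.

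*Combined protocol and SAP*

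**What the plan says.** - **Outcome.** Under Procedures (evoked pain perception): "Elapsed time until pain threshold and tolerance are reached measures evoked pain".
- **Limit.** Under Potential Study Risks, for the cold-pressor test: "all trials will be truncated at 300 seconds". In the documents on file this limit appears only in the risk section.
- **Model.** Under Analysis Plan, Statistical Analyses: "Separate mixed effects regression models will be generated for each of the continuous outcome measures of interest (pain responses, functional outcomes", fitted as linear mixed models with random intercepts and slopes, "with mean-centered baseline outcome scores serving as a covariate".
- **Distribution.** Under Analysis Plan, Preliminary Analyses: "Distributional properties will be examined to determine if variance stabilizing or normalizing transformations are required", and after normality testing, "should violations emerge (i.e., cold-pressor data are anticipated to be bimodal), transformations or non-parametric tests will be used".
- **Expected direction.** Hypothesis 1: "Subjects undergoing opioid taper will have improved pain responses over time compared to within-subject baseline". For tolerance, improvement means longer times, towards the limit.

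The Analysis Plan does not mention the 300-second limit, censoring, or how a stopped trial is scored.

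**The concern.** A participant who could have held on for 350 seconds and one who could have held on for 600 both enter the data as 300. A linear mixed model takes that value as exact. If someone is already at the limit, a further gain is invisible and part of a later fall is hidden. The baseline score used as a covariate can be capped too.

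The provision for non-normality answers a different question. Transforming the data moves the pile of capped values to another number but keeps it a pile. A rank test remains usable but ties those values and does not estimate how far tolerance moved.

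What is at stake is the size of the tolerance change. Tolerance is one of the measures behind the primary hypothesis, and the study sets out to describe how pain responses change over the taper.

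**Working it through.** **No figure in the plan to reproduce.** The documents give no share of trials at the limit, no mean tolerance and no variance. Everything below except the 300-second limit is therefore an assumption, shown as a range.

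**Step 1: direction.** For one participant with true times x and y, |min(y, 300) − min(x, 300)| ≤ |y − x|. Observed change can never exceed true change, upwards or downwards. This carries over to the group mean when participants shift in a common direction, but not otherwise. Suppose 20% fall from 400 to 320 s and 80% rise from 60 to 80 s. The true mean change is 0.2 × (−80) + 0.8 × 20 = 0 s. The capped change is 0.2 × 0 + 0.8 × 20 = +16 s.

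**Step 2: size on log seconds.** Assume log times Y are normal with mean m and SD s = √(between² + within²), with within-subject SD 0.5 and between-subject SD 0.7, 0.9 or 1.2. With c = ln 300 = 5.704 and z = (c − m)/s,

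E[min(Y, c)] = m·Φ(z) − s·φ(z) + c·(1 − Φ(z)).

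Set m so that the chosen share of baseline trials is at the limit, shift m by ± ln(fold change), and compare the capped shift with the true one.

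*Worked case: between-subject SD 0.9, 10% at the limit, 1.5-fold change.* s = √(0.81 + 0.25) = 1.030; m = 5.704 − 1.2816 × 1.030 = 4.384 (median about 80 s); true shift ln 1.5 = 0.405.

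- Baseline: 4.384 × 0.900 − 1.030 × 0.1755 + 5.704 × 0.100 = 4.336.
- After a gain (z = 0.888): 4.684. Change +0.348 against +0.405, a loss of 14%.
- After a fall (z = 1.675): 3.959. Change −0.377 against −0.405, a loss of 7%.

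*All cases, 1.25- to 2-fold change:*

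| Baseline trials at 300 s | Implied baseline median | Loss of a gain | Loss of a fall |
|---|---|---|---|
| 1% | 15–41 s | 1–3% | under 1% |
| 3% | 26–59 s | 4–8% | 1–3% |
| 10% | 57–100 s | 12–20% | 5–9% |
| 20% | 100–145 s | 22–34% | 11–18% |

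**Step 3: does it survive the planned model?** Simulations used 25 subjects, 29–38 visits, between-subject SD 0.9, slope SD 0.3, no dropout, and the capped baseline as covariate. A 1.5-fold gain shrank by 8%, 19% and 31–32% at 3%, 10% and 20% capped; a 1.5-fold fall at 10% shrank by 6%. These fall within the closed-form ranges.

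**Step 4: does a censored model repair it?** In the same simulations a censored mixed model came within 0.8% of the uncapped slope with the capped baseline as covariate, 0.3% with an added indicator for baseline at 300 s, and 0.4% with baseline as the first repeated observation. A separate simulation, with different variances and a true log change of ±0.262 at 10% capped, gave +0.248 and −0.254 from the censored model against +0.204 and −0.224 from the linear one (Monte Carlo SE of the censored means 0.014–0.026).

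**The case against.** **The share at the limit is probably low.** The Background cites cross-sectional data "showing those on opioids to have poor tolerance for experimental heat, cold and pressure pain". At 1–3% capped, a gain loses 1–8% and a fall at most 3%. With 25 subjects and the simulation inputs above, the slope's standard error is about 0.079 log units, or 19% of a 1.5-fold change (0.079/0.405) and 35% of a 1.25-fold change (0.079/0.223). At those shares the bias lies well inside sampling error for what the Abstract calls a pilot. This stands, and it is why the point is minor. It does not remove the point: Hypothesis 1 predicts movement towards the limit, and the plan expects two modes without saying where the upper one lies.

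**Capped time is a legitimate outcome.** The cold-pressor instructions are listed as an attachment but are not in the file. If they define time capped at 300 seconds as the outcome, the planned model estimates that quantity. This also stands; the Analysis Plan should then say so.

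**A reader might infer a much larger loss, on the ground that raw seconds is the working scale.** Proportional losses would indeed be larger there. But the plan names cold-pressor data as the expected violation of normality. Under the assumptions above, Shapiro-Wilk on 25 capped baseline values rejects normality of raw seconds in about 84–99.7% of data sets. Raw seconds is therefore not the realistic default, and raw-seconds losses also depend on a tail beyond 300 s that the trial cannot observe.

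**Conclusion.** The point holds as a minor one. The plan models a right-censored time as exact, and its fallback does not address the censoring. With a common direction of shift on log seconds, a gain is understated by 1–8% at 1–3% of baseline trials capped and by 12–34% at 10–20%; a fall is understated by at most 3% and by 5–18% respectively. These figures rest on log-normal times and the assumed variances. The documents do not settle which row applies, though the Background favours the low ones.

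Three stronger readings are not supported:

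- **That Hypothesis 1 loses material power.** For a 1.25-fold gain on log seconds at 3% capped, simulated power went from 73% to 71% at alpha 0.05 and from 53% to 49% at the plan's 0.05/4, with Monte Carlo error of about 3 points. Larger drops (77% to 67%, and 58% to 41%) appear at 20% capped, a share that nothing in the documents indicates.
- **That false positives are inflated.** With no true change and 10% capped, the simulated rate was 5% with and without the cap.
- **That every change is attenuated, or that all pain measures are affected.** Opposite movements across the limit can bias the group mean either way, and the 300-second limit does not apply to quantitative sensory testing.

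**What to change.** In the Analysis Plan:

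1. State that tolerance values of 300 s are right-censored.
2. Analyse tolerance on log seconds.
3. Report the share of trials at 300 s by visit.
4. Keep the planned linear mixed model, labelled as change in time capped at 300 s. Pre-specify alongside it a censored (Tobit-type) mixed model on log seconds, with random intercept and slope, for the size of the tolerance change.
5. Handle baseline identically in both models: either as the first repeated observation, or as a covariate with an indicator for baseline at 300 s.
6. If the censored model does not converge with 25 subjects, keep the random slope with a simpler covariance (uncorrelated intercept and slope), or use a subject-level bootstrap or cluster-robust errors. Do not fall back to a random intercept alone: with slope SD of 0.2–0.3 that gave roughly 11–20% false positives at a nominal 5%.

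**Cost.** A few sentences and one extra model for one outcome; no new data or visits. The censored model relies on a distributional assumption and may overshoot slightly if a second mode lies beyond the limit (5% in the one case tested, with an upper mode at 600 s). If no trial reaches 300 s and baseline is handled the same way, the two models coincide and nothing is lost.
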